# 7.2. Intervention(s) and Schedule

**Planned IMP interventions:** Letrozole oral tablet 2.5-7.5mg daily or clomifene 50-150mg daily for 5 days of each menstrual cycle for up to 6 treatment cycles, with concomitant randomisation to an escalating dose of metformin to 1500mg or placebo daily. Letrozole, clomifene, metformin and placebo will be provided as over-encapsulated tablets in numbered treatment packages. The Metformin/placebo will be provided at the same time as letrozole/clomifene.

**Dose:** The ideal dose of letrozole and clomifene for ovulation induction is not known. The choice of 2.5mg for letrozole and allowing for 2 dose escalations up to 7.5mg was made after a) careful review of the existing literature, b) a survey of UK health professionals who use letrozole for this indication, and c) reviewing the safety profile of the drug in a previous large randomised trial involving letrozole. Summary of Product Characteristics and the British National Formulary suggest a starting dose of 2.5mg. The choice of clomifene 50mg with 2 dose escalations up to 150mg was based on NICE recommendations. Our systematic review of literature and UK-wide survey of health professionals supported these regimens. The choice of metformin dose was based on our systematic review of literature and the UK-wide survey of health professionals. However, when clinicians feel the participant should be started on a higher dose because of previous cycle experience or preference, this will be allowed for a maximum of 3 tablets daily.

Route: All drugs are recommended for oral use.

**LOCI PROTOCOL** Sponsor's reference: RG\_18-272 v1.0 07-Nov-2019 Page 27 of 57 IRAS ID: 257918 EudraCT number: 2018-004641-16 ISRCTN: TBC

Regimen: Letrozole and clomifene will be given for 5 days starting on day 2 or 3 of the menstrual cycle or following the start of withdrawal bleeding for up to 6 treatment cycles (Table 1). This regimen was the most commonly used in our survey of UK health professionals. The dose of metformin will be increased gradually from 500mg daily for the 1st week, 500mg twice daily for the 2nd week, and 500mg thrice daily from the 3rd week, and continued until the end of treatment or up to 14 weeks of pregnancy (Table 2). The gradual increase of metformin was suggested by our national investigator group to minimise the side-effects of metformin. Metformin will be continued up to 14 weeks of pregnancy as this was the most commonly used regimen in our national survey of UK health professionals. However, when clinicians feel the participant should be started on a higher dose because of previous experience or preference, this will be allowed for a maximum of 3 tablets daily.

	Month 1	Month 2	Month 3	Month 4	Month 5	Month 6
Letrozole	2.5mg (1	5mg (2 tablets	7.5mg (3	7.5mg (3	7.5mg (3	7.5mg (3
	tablet per day)	per day)	tablets per	tablets per	tablets per	tablets per
			day)	day)	day)	day)
Clomifene	50mg (1 tablet	100mg (2	150mg (3	150mg (3	150mg (3	150mg (3
	per day)	tablets per	tablets per	tablets per	tablets per	tablets per
		day)	day)	day)	day)	day)

**Table 1.** Suggested dosing regimen for letrozole/clomifene. If clinically indicated, participants can be started on a higher dose from month 1, this will be permitted.

	Week 1	Week 2	Weeks 3-46*		
Metformin	500mg (1	1000mg (2	1500mg (3		
	tablet per day)	tablets per	tablets per		
		day)	day)		

**Table 2.** Suggested dosing regimen for metformin. If clinically indicated, participants can be started on a higher dose from week 1, this will be permitted. \*Maximum number of weeks if participant takes 6 months to get pregnant, then remains pregnant up to 12 weeks of gestation.

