**Interventions:** Letrozole for 5 days starting on day 2 or 3 of the menstrual cycle, plus metformin or placebo daily. Initial letrozole dose will be 2.5mg daily and increased to a maximum dose of 7.5mg daily until ovulation is confirmed, for a maximum of 6 treatment cycles. The comparison will be clomifene for 5 days starting on day 2 or 3 of the menstrual cycle, plus metformin or placebo daily. Initial clomifene dose will be 50mg daily and increased to a maximum dose of 150mg in a similar way to letrozole, for a maximum of 6 treatment cycles. The maximum dose of metformin will be 1500mg daily and continued until 14 weeks of pregnancy or until the end of the 6 treatment cycles.

**LOCI PROTOCOL** Sponsor's reference: RG\_18-272 v1.0 07-Nov-2019 Page 9 of 57 IRAS ID: 257918 EudraCT number: 2018-004641-16 ISRCTN: TBC

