# **Trial Schema**

Metformin/placebo\*\* Not ovulating < Ovulation induction 1st or 2nd cycle\* Dose escalation (max 3 tablets) Pregnant ----> Pregnancy end Ovulation induction (e.g. miscarriage) 3rd to 6th cycle 12-14 week scan Not pregnant Primary outcome: Live birth ≥ 34 weeks over 6 treatment cycles

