# Treatment details

Letrozole

Placebo

Letrozole+

Placebo

\*Clomifene/letrozole taken for up to six treatment cycles at day 2-6 or 3-7 of menstrual cycle.

Clomifene: 50mg daily with dose escalation (to 100 and 150mg daily) permitted if ovulation does not occur. Letrozole: 2.5mg daily with dose escalation (to 5 and 7.5mg daily) permitted if ovulation does not occur.

\*\*Metformin or placebo commenced concurrently with clomifene/letrozole; initial dose 500mg daily for a week escalated to 1000mg daily in week 2, then to 1500mg daily from week 3 onwards. Metformin to be continued up to 14 weeks of pregnancy.

Key secondary: pregnancy loss, number of cycles to live birth. **Exploratory secondary outcomes:** singleton live birth ≥ 34 weeks, live birth ≥ 37 weeks, gestational age at birth, ovulation rate, clinical pregnancy, birthweight, neonatal outcome at 28 days after birth, time to pregnancy. Safety outcomes: congenital anomalies, side effects to the intervention, multiple pregnancy, ectopic pregnancy and OHSS.

**LOCI PROTOCOL** Sponsor's reference: RG\_18-272 v1.0 07-Nov-2019 Page 11 of 57 IRAS ID: 257918 EudraCT number: 2018-004641-16 ISRCTN: TBC

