4.2. Trial interventions

Letrozole for 5 days starting on day 2 or 3 of the menstrual cycle, plus metformin or placebo daily. Initial letrozole dose will be 2.5 mg daily and may be increased to a maximum dose of 7.5 mg daily until ovulation is confirmed, for a maximum of 6 treatment cycles. The comparison will be clomifene for 5 days starting on day 2 or 3 of the menstrual cycle, plus metformin or placebo daily. Initial clomifene dose will be 50 mg daily and may be increased to a maximum dose of 150 mg in a similar way to letrozole, for a maximum of 6 treatment cycles.

The trial supports and documents the local clinical prescription recommended for each participant. In addition, the use of a human chorionic gonadotrophin (hCG) trigger injection following ovulation induction will be permitted and appropriately documented for participants requiring it. The maximum dose of metformin will be 1500 mg daily and continued until 14 completed weeks of pregnancy or until the end of the 6 treatment cycles.

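### Protocol section 7.2 and Table 1 show letrozole/clomifene rising to 3 tablets by month 3 without the ovulation condition stated in the summary, schema and SAP 4.2

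*Protocol*

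**What the plan says.** Three places tie escalation to ovulation.

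- Protocol, Trial Summary (Interventions): letrozole is "increased to a maximum dose of 7.5mg daily until ovulation is confirmed", and clomifene is raised in a similar way.
- Protocol, Trial Schema: the flow puts "Dose escalation (max 3 tablets" beside a not-ovulating branch. The treatment details below it read "Letrozole: 2.5mg daily with dose escalation (to 5 and 7.5mg daily) permitted if ovulation does not occur", with a matching sentence for clomifene.
- SAP 4.2: letrozole "may be increased to a maximum dose of 7.5 mg daily until ovulation is confirmed", and again clomifene follows the same pattern.

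Protocol section 7.2, where the dose and regimen are set out, does not state the condition. Its dose paragraph speaks only of "allowing for 2 dose escalations up to 7.5mg". Its regimen paragraph says the drugs are given "for up to 6 treatment cycles (Table 1") and leaves the steps to that table, which prints 1, 2, 3, 3, 3, 3 tablets a day across months 1 to 6. The caption is "Suggested dosing regimen for letrozole/clomifene. If clinically indicated, participants can be started on a higher dose from month 1, this will be permitted". Section 7.2 also lets a clinician start a woman higher "because of previous cycle experience or preference, this will be allowed for a maximum of 3 tablets daily".

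Section 6.2.2, on blinding, illustrates matched tablet counts with the same 1-2-3 steps and no ovulation condition. Section 7.4 allows clinicians to vary the dose in line with usual practice and requires the dose and the reason to be recorded. SAP 4.2 adds that the trial supports and documents the local prescription.

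**The concern.** A site looking up the dose will go to section 7.2, and there the dose rises with time and never stops for ovulation. A literal reading is plausible for four reasons.

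- Table 2, directly below, is a purely time-driven metformin step-up with an almost identical caption. Nothing tells the reader that Table 1 works differently.
- The Table 1 caption covers starting higher, but not holding the dose.
- Dispensing is marked at baseline only (Table 3), and the pack covers all six letrozole/clomifene cycles (section 7.7.2).
- Section 7.1 sets no trial visit between cycles at which the dose would be reviewed, although routine clinic contact may still occur.

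At stake is dose exposure. A woman who already ovulates on 1 or 2 tablets could be moved up when the stated trigger does not call for it, in a trial that lists multiple pregnancy and ovarian hyperstimulation among its safety outcomes (section 8.1.3.3).

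**Working it through.** The plan gives no total dose, so there is no figure of its own to reproduce. The daily steps do agree throughout: 1, 2 and 3 tablets are letrozole 2.5, 5 and 7.5 mg, or clomifene 50, 100 and 150 mg, with a maximum of 3 tablets. Only the trigger differs.

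**Step 1: the texts side by side**

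| Place | Steps | Ovulation condition stated? |
|---|---|---|
| Trial Summary | up to the maximum dose | yes |
| Trial Schema and treatment details | two steps, maximum 3 tablets | yes |
| SAP 4.2 | may rise to the maximum dose | yes |
| Section 7.2 text | two escalations allowed | no |
| Section 7.2, Table 1 and caption | 1, 2, 3, 3, 3, 3 | no |
| Section 6.2.2 example | 1, 2, 3 | no |

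**Step 2: how far apart the two readings can be**

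Inputs: 5 days per cycle and at most 6 cycles (section 7.2); daily tablets from Table 1; tablet strengths of 2.5 mg letrozole and 50 mg clomifene. The woman starts on 1 tablet and does not conceive in six cycles. Under the stated trigger she stays on the dose at which she ovulates.

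Total tablets = 5 × (sum of daily tablets over the cycles).

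- Table 1 taken literally: 5 × (1+2+3+3+3+3) = 5 × 15 = 75.
- Ovulates on 1 tablet, dose held: 5 × (6 × 1) = 30. Excess 75 − 30 = 45; ratio 75/30 = 2.5.
- Ovulates on 2 tablets, dose held: 5 × (1 + 5 × 2) = 55. Excess 75 − 55 = 20; ratio 75/55 = 1.36.
- Needs 3 tablets or never ovulates: 5 × (1 + 2 + 4 × 3) = 75. Excess 0.

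In milligrams, for the woman who ovulates on 1 tablet: letrozole 75 × 2.5 = 187.5 against 30 × 2.5 = 75; clomifene 75 × 50 = 3,750 against 30 × 50 = 1,500.

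**Step 3: conception shrinks the gap**

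For a woman who ovulates on 1 tablet, literal reading against stated trigger:

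- conceives in cycle 1: 5 against 5;
- conceives in cycle 2: 5 × (1+2) = 15 against 10;
- conceives in cycle 3: 5 × (1+2+3) = 30 against 15.

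**Step 4: average over women**

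Let p1 and p2 be the shares who ovulate on 1 and on 2 tablets. Among women who start on 1 tablet and complete six cycles without conceiving, the mean excess is 45 × p1 + 20 × p2. The documents give neither share, so all that can be stated is the range: 0 tablets (p1 = p2 = 0) to 45 tablets (p1 = 1).

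**The case against.** The strongest reply is that the condition has merely not been repeated. The same protocol states it in the summary and schema. Table 1 is labelled as suggested, and the 7.2 dose paragraph permits escalation without ordering it. The 6.2.2 text is an example about blinding. The 1-2-3-3-3-3 pattern also fits the schema if Table 1 is read as the path for a woman who does not ovulate. Section 7.4 and SAP 4.2 leave the dose to clinical judgement, so a clinician who sees ovulation can hold it. And the protocol supplied is v1.0 from 2019, while the SAP describes later changes, so the current wording may differ.

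Much of this stands. The texts can be reconciled, and a reader who inferred that the protocol mandates over-dosing would be wrong. What does not fall away is that 7.2 never says Table 1 is the non-ovulating path, and that it sits above a table that really is time-driven.

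Two other inferences should be resisted. One is that the month headings in Table 1 are a separate error. Section 6.2.2 uses month as shorthand when describing tablets per cycle, and the 240-day limit is a conception window counted from randomisation (SAP 9.4), so no cycle length can be derived from it. The other is that, because both drugs share the same tablet steps, any effect must be equal across them. Excess exposure depends on p1 and p2, which may differ between letrozole and clomifene. The documents do not settle it either way.

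**Conclusion.** The inconsistency is real and worth fixing. Section 7.2 with Table 1, and the 6.2.2 example, omit the ovulation condition that the summary, schema and SAP 4.2 state. The arithmetic bound is 75 tablets against 30 for a woman who ovulates on 1 tablet, and 75 against 55 for one who ovulates on 2. It assumes a 1-tablet start, six cycles without conception, and a site that follows Table 1 literally and makes no use of section 7.4 or local prescription. Relaxing any of these can only leave the gap unchanged or reduce it.

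A reader might go further and infer extra multiple pregnancies or hyperstimulation. The documents give no dose-risk figure and no indication of how often sites would read the table this way, so neither is claimed. Nor do they show any bias in the treatment comparisons.

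One limit applies: the patient-pathway figure (Figure 7) could not be seen, though the point does not rest on it.

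**What to change.** Add a note to the Table 1 caption along these lines: *Escalation path for a woman who does not ovulate. If ovulation occurred in the previous cycle, keep that dose unless the clinician decides otherwise and records the reason (section 7.4). If ovulation was not assessed, do not increase automatically.* In the 6.2.2 example, add that the steps apply *if ovulation does not occur*.

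The clause on unassessed cycles is needed because day-21 progesterone, though marked for each of months 1 to 6 in Table 3, is done only where applicable, and ultrasound is optional and marked for month 1 only. The clinician exception keeps the note within the discretion that section 7.4 and SAP 4.2 already give.

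The cost is a small protocol amendment and a site memo, with no added testing. If the sponsor judges the change substantial, section 19 requires ethics committee and HRA approval. If dosing is already complete, rewording cannot change what was taken. In that case, report tablets per day by cycle and arm in the intervention table (SAP 7.1), unless the separate template report already does so.

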# 7.3. Drug Interaction or Contraindications

The following drugs and contraindications will be in place for this trial and women will be excluded if:

- Pregnant or breastfeeding women
- Liver disease or a history of liver dysfunction
- Hormone-dependent tumours
- Abnormal uterine bleeding of undetermined origin and in the presence of an ovarian cyst, except polycystic ovary, since further enlargement of the cyst may occur
- Acute conditions with the potential of altering renal function, including:
  - Dehydration
  - o Severe infection

 LOCI PROTOCOL
 Sponsor's reference: RG\_18-272
 v1.0 07-Nov-2019
 Page 28 of 57

 IRAS ID: 257918
 EudraCT number: 2018-004641-16
 ISRCTN: TBC

- Shock
- Intravascular administration of iodinated contrast agents
- o Acute or chronic disease which may cause tissue hypoxia such as:
  - Cardiac or respiratory failure
  - Recent myocardial infarction
  - Shock
  - Hepatic insufficiency
  - Acute alcohol intoxication
  - Alcoholism
  - Lactation
  - Any type of acute metabolic acidosis (such as lactic acidosis, diabetic ketoacidosis) and severe renal failure (GFR <30 mL/min)

- Other medications known to affect reproductive function or metabolism, including:
  - Oral contraceptive pills (OCPs)
  - o GnRH agonists and antagonists
  - Anti-androgens
  - o Gonadotropins
  - Anti-obesity drugs
  - Somatostatin
  - Diazoxide, ACE inhibitors
  - Calcium channel blockers

We will allow a 2-month washout period for subjects who desire to participate and discontinue exclusionary medications (most commonly OCPs), and a period of observation or treatment for correctable conditions

All drugs are contraindicated for patients with hypersensitivity to letrozole, clomifene and metformin or to any of their excipients.

Concomitant therapy will be at the discretion of the care-providing clinicians, and all concomitant treatments and medications relevant to ovulation induction (e.g. inositol) will be documented in the electronic data capture system.

### 7.4. Treatment Modification

If any patient reports serious adverse effects from any of the trial drugs, or wishes to discontinue for any reason they will be allowed to and the reasons carefully logged. Clinicians may vary the dosage of any of the trial mediations in line with standard clinical practice. Both the dosage and the reasons for the change will be recorded.

## 7.5. Cessation of Treatment / Continuation after the Trial

A participant may be withdrawn from trial treatment if it becomes medically necessary in the opinion of the investigator(s) or clinician(s) providing patient care. In the event of such premature treatment cessation, LOCI study personnel will make every effort to obtain and record information about the reasons for discontinuation and any adverse events, and to follow up all safety and efficacy outcomes as appropriate.

 LOCI PROTOCOL
 Sponsor's reference: RG\_18-272
 v1.0 07-Nov-2019
 Page 29 of 57

 IRAS ID: 257918
 EudraCT number: 2018-004641-16
 ISRCTN: TBC

A participant may voluntarily decide to cease taking the LOCI trial treatments at any time. If a participant does not return for a scheduled visit, attempts will be made to contact her and (where possible) to review compliance and adverse events. If a woman decides after randomisation that she does not wish to continue her pregnancy, she may withdraw herself from the trial. We will aim to document the reason(s) for self-withdrawal.

Clear distinction will be made between withdrawals from trial treatments whilst allowing further follow-up, and any participants who refuse any follow-up. If a participant explicitly withdraws consent to any further data recording then this decision will be respected and recorded on the electronic data capture system. All communications surrounding the withdrawal will be noted in the participant's records and no further data will be collected for the participant.

# 7.6. Treatment Supply and Storage

# 7.6.1. Treatment Supplies, Packaging and Labelling

Investigational medicinal products will be procured, assembled, packed and quality assured by MODEPHARMA Ltd, a global clinical services company we have used for previous clinical trials. MODEPHARMA Ltd holds a Manufacturer Licence for tablets and capsules under the Good Manufacturing Practice requirements (GMP; EU Directive 2003/94/EC) and in compliance with Good Clinical Practice (GCP; Clinical Trials Directive 2001/20/EC) Annex 13 requirements. MODEPHARMA Ltd does not hold the Marketing Authorisation for the trial IMPs.

# 7.6.2. Drug Storage

The study drugs will be stored and dispensed from the pharmacies of participating hospitals. All pharmacies will comply with the relevant guidelines and regulations including the Duthie report of 1988 and the Royal Pharmaceutical Society Practice Guidance on Pharmacy Services for Clinical Trials, 2005. Clinical trial medication will be dispensed against an appropriate prescription form that carries the title the LOCI Trial, the EudraCT number, investigator and sponsor name, instructions for use and a unique trial number according to GCP Annex 13 requirements. Detailed dispensing records will be kept by each dispensing pharmacy. The SmPC for clomifene and metformin state that they should be stored below 25°C. Shipments from MODEPHARMA Ltd will be temperature-monitored. Participants will be advised to keep their trial treatment packs away from extremes of temperature.

# 7.7. Accountability and Compliance Procedures

## 7.7.1 Compliance

The dispensing of the LOCI trial drugs will be recorded in the pharmacy drug accountability log. The Trial Manager will periodically request the trial drug chart to verify that the dispensing system is being followed. Any deviations from the protocol schedule should be logged locally and both the PI and Trial Office informed.

**LOCI PROTOCOL** Sponsor's reference: RG\_18-272 v1.0 07-Nov-2019 Page 30 of 57 IRAS ID: 257918 EudraCT number: 2018-004641-16 ISRCTN: TBC

Participants will be asked to return completed, partially used and unused treatment packs to the trial centres at their routine follow-up hospital appointments (e.g. fertility clinic appointments, 12 week booking scan). The research nurse at each local centre will receive the empty/partially used/unused treatment packs, and record the information for each trial participant, in the database. To monitor compliance, women who fail to return the treatment packs, whether empty or not, will be contacted by telephone or email by the research nurse for advice and support. The research nurse will ask the participant for an honest assessment of how many of the trial drugs were taken and record this information.

# 7.7.2. Accountability

At randomisation, the trial treatment number will be provided and this reference will correspond to a trial treatment pack available in the local hospital pharmacy. The pharmacist will receive notification of the name and trial number of the randomised woman and will prepare the trial treatment pack for dispensing. The trial treatment packs will cover six treatment cycles for clomifene or letrozole and seven calendar months for metformin or placebo. A separate pack will contain 14 weeks supply of metformin or placebo to cover the time from conception up until 14 weeks of gestation for women that conceive while on the trial.

The local pharmacist should keep accurate records of trial drugs dispensed using a pharmacy log provided by the LOCI Trial Office. Trial drugs must be kept in the packaging supplied and under no circumstances used for other participants or non-participants.

**LOCI PROTOCOL** Sponsor's reference: RG\_18-272 v1.0 07-Nov-2019 Page 31 of 57 IRAS ID: 257918 EudraCT number: 2018-004641-16 ISRCTN: TBC

# **LOCI Patient Pathway**

[figure not shown]

Figure 7. Patient pathway.

 LOCI PROTOCOL
 Sponsor's reference: RG\_18-272
 v1.0 07-Nov-2019
 Page 32 of 57

 IRAS ID: 257918
 EudraCT number: 2018-004641-16
 ISRCTN: TBC

# 8. OUTCOME MEASURES AND STUDY PROCEDURES

#### 8.1. Trial Outcomes

## 8.1.1. Internal pilot outcome

- 1. Open a minimum of 7 recruiting hospitals within six months of the first recruiting hospital being activated.
- 2. Recruit a minimum of 72 patients within six months of the first recruiting hospital being activated.

